4.3.1 VITAMIN D SUPPLEMENTATION

It is recommended that all patients be sufficient for Vitamin D (25-OH Vitamin D) throughout the trial, as standard of care. Those with severe Vitamin D deficiency (< 10 ng/ml or 25 nmol/L) are excluded from the trial, although they can be re-screened after treatment with vitamin D. For all other patients, the following Vitamin D supplementation is recommended:

- Vit D insufficient (11-30 ng/ml) treat with 1,000 IU Vit D daily
- Vit D sufficient (31-60 ng/ml) treat with 400 IU Vit D daily
- Vit D level > 60 ng/ml, no need for additional supplementation
- Physicians will have the option to use differing doses of Vitamin D if they deem to be clinically indicated.

4.4 ADMINISTRATIVE ROLE OF OPERATIONS CENTER (UAB)

The Operations Center for the NF Clinical Trials Consortium, funded by the DOD, will provide administrative support for this clinical trial. In addition to what is described throughout this protocol, it will organize and oversee the clinical trial initiation meeting wherein all aspects of the protocol will be finalized and standard operating procedures fully elucidated. The Operations Center will continue to organize annual face-to-face meetings, and administer all teleconferences. There will be a minimum of one teleconference call per month, and the co-PIs on this protocol will also join the executive committee monthly teleconference call for the NF Clinical Trials Consortium. Data-sharing between sites will be overseen by the DMAC, and approvals for human subjects research will be orchestrated between the institutional review boards from the University of Alabama at Birmingham and the Department of Defense prior to distributing to all other participating sites for approval at their respective institutions.

Each participating institution is required to maintain a current MPA or FWA in order to participate in government-sponsored Group research. The files will be copied or made available for review by authorized persons as required for conduct of this trial.

Continuing Reviews, Amendments and Consents

The PI from each participating institution will provide the NF Consortium Operations Center with a copy of IRB approval of all amendments to the protocol or consent. The NF Consortium Operations Center will provide these institutional reviews to the USAMRMC ORP HRPO. As this trial receives funding by the US Army, approval of all protocol amendments will be obtained from the USAMRMC ORP HRPO in addition to the institutional IRB prior to implementation.

4.5 Data Collection and Data Handling

The trial is being conducted by the NF Clinical Trials Consortium. Electronic Case Report Forms (eCRFs) developed by the NF Consortium Operations Center will be used for submitting

clinical data to the DMAC. Data must be submitted to the DMAC within two weeks of completing each required evaluation while the patient is on study.

The **Radiology Review Panel (RRP)**, comprised of a group of 4 physicians (3 radiologists and 1 orthopaedic surgeon) from Scottish Rite Hospital in Dallas will independently review all radiographs using the RUST scoring system. The RRP will receive radiographic studies with clinical trial study identifiers on a CD, which will then be uploaded with only study identifiers onto the reading system that allows each member to score the radiographs, blinded to other panel member's scores. After individual scoring is completed, the panel will meet as a group and assign a consensus score to each radiograph. The score sheets will be entered into a database interface created by the data management center.

The **Biospecimen Allocation Committee (BAC)** will oversee the review of applications for use of biological specimens. Once decisions have been made by the BAC to approve access to samples, the TSRH Tissue Processing Facility will distribute to the investigator using standard operating procedures. The BAC will be comprised of participants of the rhBMP-2 tibial pseudarthrosis clinical trial, one representative from TSRHC, members of the steering committee of the NF Clinical Trials Consortium, **operating independently of the Operations Center, and other members from outside the Consortium, as deemed appropriate**. Guidelines for the BAC review process will be finalized prior to enrollment of patients for the study.

Representatives from the FDA, and the U.S. Army Medical Research and Materiel Command will have access to the data and research records.

Role of Data Management

Instructions concerning the recording of study data on CRFs will be provided by the Data Management Center (DMAC) of the NF Operations Center. It is the responsibility of the DMAC to assure the quality of data for their study. This role extends from protocol development to generation of the final study database.

The DMAC has extensive experience in data management, currently managing 18 national/international collaborative trials/studies. For the purpose of the proposed trial, they will be using an existing electronic Data Entry System (eDES) that serves as a shared platform that seamlessly supports the data management needs across the spectrum of these projects. This system has a common administrative site and a consistent platform that reduces the enormous effort required to initiate, manage, maintain and validate multiple individual applications used, particularly those involved with FDA oversight, where extra requirements apply. The electronic Data Entry Management Systems (eDEMS) and methodologies employed for the other NF studies will be built on the existing highly successful MITS Suite.

The MITS Suite consists of the MITS Studio (electronic Data Entry Management System [eDES] Authoring Tool) and the Testing Framework. The architecture is designed to efficiently accommodate trial organizations, that have multiple projects operating across a common set of clinics. The MITS Studio provides a structured design environment that ensures repeatable results across trials by utilizing a common set of vetted software components. Our systems are designed to adhere to FDA 21 CFR Part 11 guidelines in developing the authoring and testing framework components and are compliant with the evolving FDA CDISK standards.

All centers participating in subject evaluation for this trial will complete mandatory electronic training modules developed by the DMAC prior to performing any of the study assessments to ensure compliance with 21 CFR11.10(i).

Data and Center Audits

The trial will be audited by the NF Consortium Operations Center for compliance and safety. Independent monitors will visit participating sites and review case report forms and source documentation. Missing or spurious information and protocol deviations will be communicated in a report to the clinical site and trial coordinating center. Protocol deviations, which may result in compromise to safely administer medical device, or to determine study endpoints will be reported promptly to the USAMRMC ORP HRPO.

All unexpected and serious adverse events will be forwarded to the Medical Monitor, the Study PI and the USAMRMC ORP HRPO by the NF Clinical Trials Consortium Operations Center.

5.0 TREATMENT PROGRAM

5.1 Agent Information: Bone Morphogenetic Protein -2

rhBMP-2 is the active agent of the INFUSE® device, which consists of two parts: a recombinant human protein (rhBMP-2) to stimulate bone healing, and an absorbable collagen sponge (ACS) made from cow (bovine) collagen that is soaked with the protein. rhBMP-2 is the active agent in INFUSE®. It is a disulfide-linked dimeric protein molecule with 2 major subunit species of 114 and 131 amino acids. Each subunit is glycosylated at one site with high-mannose-type glycans. rhBMP-2 is produced by a genetically engineered Chinese hamster ovary cell line. The INFUSE® Bone Graft device is designed to be used along with internal stabilization with an intramedullary rod or nail to help heal fractures of the lower leg bone (tibia).

Further details are in Sections 2.1 and 2.2

5.2 Surgical Protocol for Treatment of Tibial Pseudarthrosis

The surgical protocol to be used is outlined in [name] et al. [2010] and includes tibial osteotomy with resection of the pseudarthrosis tissue, followed by placement of an intramedullary rod which provides rigid fixation. The exact type of rod used will vary based on availability in different centers and different countries, but will be a rigid rod similar in size and configuration to a Williams or Rush type rod. In no cases will the intramedullary canal be reamed. Fixation of the ankle will be at the discretion of the surgeon regardless of the patient's age. Bone grafting will be performed with autogenous bone from iliac crest placed into the excised pseudarthrosis site. As per instructions provided by the provider of the INFUSE® kit device (Medtronic), rhBMP-2 will be applied to an absorbable collagen sponge. The sponge is applied as an onlay, bridging the area of pseudarthrosis. The application of the collagen sponge saturated with rhBMP-2 is shown below.

Figure 5: Application of INFUSE at surgery.

FIG 1A.

FIG 1B.

The BMP-2 soaked collagen sponge is placed around bone junction at the tibial osteotomy site. After autogenous bone graft has been placed in the tibial osteotomy site, the collagen sponge is wrapped around both the tibia and the bone graft.

The dosing of rhBMP-2 is restricted to the size of absorbable collagen sponge used in the surgical field. The concentration of rhBMP-2 in the sponge is standardized to 1.5 mg/cc sterile water on the sponge. For the purposes of this trial, the size of INFUSE bone graft used will be adjusted for weight. Patients less than 30 kilogram weight will receive a small INFUSE package (4.2mg of rhBMP-2 on 2 collagen sponges, with concentration of 1.5 mg/cc); those greater than or equal to 30kg weight will receive a medium INFUSE package (8.4 mg BMP-2 and 4 collagen sponges, with concentration of 1.5 mg/cc). Higher doses were avoided due to the concern that higher doses of rhBMP-2 can induce osteoclasts that initiate bone resorption, and to decrease theoretical risk of carcinogenicity possibly seen with very high doses of BMP-2.

In addition to surgical management of the tibia, the ipsilateral fibula will be assessed radiologically and decisions for surgical intervention will be incorporated into the operative strategy to stabilize the tibia. In cases where the fibula is intact, the fibula will undergo osteotomy with intramedullary fixation in order to shorten the fibula and prevent distraction by the intact fibula. In cases where the fibula was severely resorbed ("sucked candy" configuration on Xray), an osteotomy is not necessary and intramedullary fibular fixation is impossible to perform.

Patients will be immobilized with above-the-knee cast or spica cast for a minimum of 3 months post-operatively. Managing surgeons can decide on an individual basis whether a patient requires casting for longer than 3 months. After the cast is removed, patients will be permanently braced (24 hours per day) in a custom-made orthosis, either above-the-knee or below-the-knee, at the discretion of the surgeon. Radiographs of the lower leg and ankle will be performed at 6 weeks, 3, 6, 9, and 12 months after surgery at times corresponding to follow-up evaluations and cast changes.

Summary of Surgical Protocol:

- Tibial osteotomy
- Resection of pseudarthrosis tissue
- Fibular osteotomy if intact fibula
- Placement of intramedullary rod providing rigid fixation
 - Williams, Rush, or other type
- Ankle fixation at discretion of the surgeon
- Placement of iliac crest autograft at the surgical site
- If randomized to BMP-2 treatment group:
 - Reconstitution of BMP-2 in sterile water as per package instructions (at least 15 min before application) and applied to the collagen sponge(s).
 - A small INFUSE package (4.2 mg total BMP-2 and 2 sponges with concentration of 1.5 mg/ml) will be used for patients weighing < 30 kg
 - A Medium INFUSE package (8.4 mg total BMP-2 and 4 sponges, with concentration of 1.5 mg/ml) will be used for patients weighing ≥ 30 kg. INFUSE bone graft sponge is wrapped around the tibial osteotomy site and autograft.
- Incision is closed
- Above-the-knee or spica cast x minimum of 3 months

Rehabilitation Protocol

- All patients will be in an above-the-knee or spica cast for a minimum of 3 months
- Recommend no weight-bearing on affected leg for 3 months post-op
- Further cast immobilization may be used if the surgeon interprets the radiographs as having too little callus formation at the tibial pseudarthrosis site
 - Cast time may be extended in 4-6 week intervals, followed by radiographic re-evaluation until satisfactory healing has been achieved.
 - If casting is required beyond 3 months, it may be below-the-knee instead of above-the-knee.
- Braced (above or below knee) with partial weight-bearing beginning at 3 months
- Knee mobilization exercises beginning at 3 months (or after removal of cast if later than 3 months).
- Full weight-bearing (braced) based on X-ray appearance (RUST score of 9 or greater)
- No sports participation until 1 year post-operative and with brace in situ.
- Individual questions about rehabilitation protocol may be addressed to the two study surgeons (Drs. [name] and [name]).

5.3 Protocol to Radiographically Score Tibial Healing (RUST score, Primary Outcome Measure; Specific Aim 1)

The assessment of tibial healing in patients with tibial pseudarthrosis will be based on radiographic evidence of union by determination of cortical continuity on X-ray and scoring by a novel system called the Radiographic Union Score for Tibial fractures (RUST) score [Whelan et al., 2010]. This validated method assigns a score to a set of anteroposterior (AP) and lateral (Lat) radiographs based on healing at each of the 4 cortices. The lateral and medial cortices are denoted on the AP radiograph and the anterior and posterior cortices on the lateral radiograph. A score of 1-3 is assigned based on the persistence of the fracture line and the presence or absence of callus formation. If all 4 cortices are evaluable then scores range from 4 (non-union all bone columns) to 12 (complete union of all 4 bone columns). As this method was validated in fractured normal tibias, any lucency was considered residual fracture. However, in these patients there is known underlying dysplasia affecting the appearance of the bone underlying the osteotomy; therefore an intact peripheral cortex with residual intramedullary dysplasia will be considered healed. A cortex that is not visualized due to eccentric overlying hardware will be given a value of 1.

Scoring system:

1 = no new calcification, or rod eccentricity precludes evaluation

2 = new calcification or callus present

3 = smooth continuous outer cortex, even if underlying lucency

Total score ranges from 4 to 12.

For the purpose of this study, a RUST score of 9-12, with at least 2 evaluable cortices having a score of 3, will be considered to be healed, and a successful outcome.

Figure 6: RUST scoring

Figure showing partial bridging and callus formation of all 4 cortices.

RUST score = 2+2+2+2 = 8

Implementation of the RUST scoring method as the sole criterion for tibial fracture healing will enable the same radiology review panel (RRP) of 4 individuals to score both prospective cases and historic controls. The total RUST point score range is 4 to 12. Additionally, information on functional status will be collected before surgery, and at each subsequent evaluation after surgery, as outlined in Johnston [2002] and [name] et al., [2010]. This includes status of the ability to walk with weight-bearing, use of orthotic support, presence of pain, point tenderness at the site, level of physical activity, additional surgery of the ipsilateral leg in addition to radiographic evidence of union, knee and ankle motion, foot position, leg-length discrepancy, and overall clinician satisfaction.

5.4 QUALITY OF LIFE ASSESSMENTS

Pediatric Outcome Data Collection Instrument (PODCI)

An important outcome measure of clinical trials in treatment of tibial pseudarthrosis is quality of life. Many individuals with TPA undergo multiple surgical interventions with long rehabilitation times, precluding their participation in school and recreational activities. In preliminary studies performed by collaborators [name] and [name], an outcomes trial led by [name] (Shriners Research Grant #9165; Multi-Center Study of Outcome of Tibial Dysplasia in NF1 Patients) used the pediatric outcome data collection instrument (PODCI) to evaluate the quality of life of individuals with NF1, with and without tibial dysplasia. The PODCI consists of five domains, with a number of items in each domain [Daltroy et al, 1998; Vitale et al, 2001]. Twenty-three individuals with NF1 with tibial dysplasia were compared to 63 NF1 individuals without tibial dysplasia. Notably, the Basic Mobility normative scores, the Sports and Physical Function scores, and Global Functioning were significantly decreased ($p<0.001$) in NF1 with tibial dysplasia with the mean score for cases about one-third of controls [Stevenson and [name], 2009]. The PODCI has also been reviewed by the REINS committee (Response Evaluation in Neurofibromatosis and Schwannomatosis), and found to be an appropriate outcome measure for this population. **These data demonstrate that the PODCI is an effective QOL measure that can be used to investigate outcome for treatment of TPA in the NF1 population**, and can accompany more traditional clinical measures such as union, range of motion, leg length discrepancy, and limitation of walking distance. Other measures of quality of life have been implemented for the NF1 population [Krab et al., 2009] and the orthopedic community [Vitale et al., 2001; Furlong et al., 2005]; however, these measures have not been applied to the pediatric NF1 population with orthopedic issues.

- Quality of Life will be assessed using the Pediatric Outcome Data Collection Instrument (PODCI) questionnaire. The PODCI is a comprehensive orthopedic-specific instrument (Pencharz et al., 2001) comprised of over 100 questions and takes 15-20 minutes to

complete. Quality of Life Questionnaires are to be completed by patient and parents as follows at baseline, at 6 months, and at 12 months.

- PODCI Pediatrics-parent/child: baseline and follow-up (completed by the parent for all children 2-10 years old).
- PODCI Pediatrics-parent/adolescent: baseline and follow-up (completed by the parent for all adolescents 11-18 years old).
- PODCI Pediatrics-adolescent baseline and follow-up (completed by patient between 11 and 18 years old)
- In addition to the PODCI, pain intensity will be assessed using the Faces Pain Scale-Revised (FPS-R) for patients aged 4 years and older, at baseline and at 6 weeks, 3 mos, 6 mos, and 12 mos after surgery. This is a self-report pain scale which has been validated for use in research, in patients as young as 4 years. Children chose one of 6 faces as indicating their current pain. There are no validated self-report pain scales for children between 2 and 4 years. Additional pain measures, including pain interference, are included in the PODCI for all ages participating in the study.

5.5 FUNCTIONAL ASSESSMENT: Ten Meter Timed Walk

The **timed 10 meter walk test** is a functional outcome measure that has been used extensively in the fields of rehabilitation medicine, neurology, and orthopaedics. In this well-validated, easily administered test, a 10 meter (32.8 feet) hallway is measured and marked, with starting line and end line. The patient is given instructions either to walk the distance at his/her normal, comfortable speed, or as quickly as safely possible. The walk is timed using a standard stopwatch, and results are recorded in seconds. The patient performs the test 3 times, and the mean value of the 3 trials is used as the result. Results from this test will be compared for individuals at baseline, 6 mos after surgery, and 12 mos after surgery, and will be used as a secondary outcome measure. The timed 10 meter walk is easy to perform in a clinic setting without special equipment such as a gait analysis lab. The test has been used extensively in studies of muscular dystrophy, spinal cord injury and cerebral palsy, and has been validated from ages 4 years through adults [Pirpis et al, 2003]. It has also been used as an outcome measure in a Phase 3 clinical trial for multiple sclerosis [Cohen et al., 2001]. A 20% change in walking speed is considered to be significant. The test can be performed while a patient is in a brace or other adaptive device. This test and other functional outcome measures have recently been reviewed extensively by the REINS committee, and based on its reliability and ease of use was recommended as a secondary outcome measure for NF trials assessing ambulation.

The 10 meter Timed Walking Test will be performed before surgery, and at 6 months and 12 months post surgery. The test can be performed with the leg braced, and any bracing or other assistive device will be recorded at each time point. The test will be performed 3 times, and the mean of the 3 times (in seconds) will be recorded as the final score at each visit.

Data will be entered into eDES at the clinical sites and sent electronically to the DMAC for subsequent analysis.

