4.2.4 Informed Consent/Accent

The investigational nature and objectives of the trial, the procedures and treatments involved and their attendant risks and discomforts, and potential alternative therapies will be carefully explained to the patient or the patient's parent(s) or guardian if the patient is a child, and a signed informed consent and assent will be obtained according to both institutional and U.S. Army Medical Research and Materiel Command, Office of Research Protections, Human Research Protection Office (USAMRMC ORP HRPO) guidelines. Patients between the ages of 2 – 18 years at time of surgery will be eligible for consent. The principal investigator at the enrolling site will be responsible for obtaining informed consent. The study trial coordinator can provide information on the study and obtain consent if qualified as determined by the PI of the site. Most patients in this study will be less than 7 years of age. Those older than 7 will undergo age-appropriate assent tailored for both children aged 7-12 years, and for those aged 13-17 years (or until the age of majority in the state of the clinical center).

A study participant should sign the institution's HIPAA Consent.

A study participant should sign the institution's Release of Medical Information Waiver.

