4.3 PATIENT ELIGIBILITY/ INCLUSION AND EXCLUSION CRITERIA

Any individual with NF1 based on either NIH-diagnostic criteria or congenital pseudarthrosis of the tibia plus documented mutation in the *Nf1* gene is eligible for this study. Furthermore, decisions for surgical intervention must be made on a clinical basis with a determination that intramedullary rod plus autogenous bone graft is the most appropriate management approach for that individual patient. Patients may be enrolled only at the time of 1st or 2nd surgery for tibial pseudarthrosis, not subsequent surgeries. Candidates must be able to travel to an orthopedic surgical site that is participating in the study. Patient insurance must approve coverage of the surgical procedure and short-term post-operative care at the orthopedic center performing the operation, or patients can use a self-pay procedure to cover the surgical and hospital costs associated with the surgical procedure.

Inclusion Criteria for all patients:

- All patients who do not have a documented *NF1* mutation must meet the clinical diagnosis of NF1 using the NIH Consensus Conference criteria. In addition to tibial pseudarthrosis, one or more of the following diagnostic criteria for NF1 must be present:
 - Six or more café-au-lait spots ($\geq 0.5\text{cm}$ prepubertal; $\geq 1.5\text{cm}$ postpubertal)
 - Freckling in the axilla or groin
 - Optic pathway glioma
 - Two or more iris Lisch nodules
 - Two or more neurofibromas or one plexiform neurofibroma
 - A first-degree relative with NF1
- Patients must have tibial pseudarthrosis that has the potential to cause significant morbidity. Radiographic findings (AP & lateral leg radiographs) must support the diagnosis of tibial pseudarthrosis with chronic non-union.
- Age between 2 years and 18 years of age at time of study entry.
- Performance Level: Karnofsky $\geq 50\%$ for patients > 10 years of age and Lansky ≥ 50 for patients ≤ 10 years of age (Appendix III).
- Prior Therapy:
 - Patients who have undergone 1 previous surgery for tibial pseudarthrosis repair will be eligible to enter the study if they have refracture. Use of BMP-2 in the prior surgery is permitted, however patients with prior exposure must be screened for antibodies to BMP-2, bovine collagen, and rhBMP-2 neutralizing antibodies.

- Prior use of BMP-2 is allowed but will be recorded as a possible compounding factor.
- Patients who have had 2 or more prior surgeries for pseudarthrosis repair are ineligible

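### The 10 meter walk has no score for a child whose leg prevents the walk, so failure to recover and recovery from not walking can both go unseen

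*Combined protocol and SAP*

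**What the plan says.** Section 5.5 names the timed walk as a secondary outcome measure. On the unit it says "The walk is timed using a standard stopwatch, and results are recorded in seconds", and on the score, "the mean of the 3 times (in seconds) will be recorded as the final score at each visit"; section 5.8 repeats the scoring rule. On timing: "The 10 meter Timed Walking Test will be performed before surgery, and at 6 months and 12 months post surgery". The only benchmark for change is on another scale: "A 20% change in walking speed is considered to be significant".

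The same section says the test "has been validated from ages 4 years through adults". Entry (section 4.3) is wider: "Age between 2 years and 18 years of age at time of study entry". Section 4.2.4 adds: "Most patients in this study will be less than 7 years of age". Neither section 5.5, section 5.8 nor Appendix I sets a lower age for the walk.

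The Analyses part of section 6.2 groups the walk with the quality-of-life measures. It plans paired t-tests on change from before treatment through 12 months, and mixed models for longer-term change. The missing-data paragraph of section 6.2 deals with the 12-month radiograph only. If 5% or more of the data are missing it calls for multiple imputation, and the 12-month walk is one of the predictors. No section says what to enter for a child who cannot complete the walk.

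**The concern.** A time exists only if the child finishes the distance. A child who is still in a cast, has a non-union or has refractured may not finish, and then has no value. The reason is the condition under treatment, so the missing values are tied to healing.

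This can mislead in two directions. A child who has not recovered disappears from the follow-up data. A child who could not walk before surgery and can walk afterwards has no change score, so a large improvement disappears as well. A comparison of the remaining times describes only children well enough to walk.

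There is also a route to the primary analysis: a child without a 12-month walk has a gap in a predictor of the RUST imputation model.

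**Working it through.** The documents give no sample size, SD or effect size for the walk, so there is no planned figure to reproduce. The check is a reading of the rules plus simple arithmetic.

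**1. Can a child be without a time?**
- At entry: section 4.3 excludes only a condition other than the pseudarthrosis that prevents ambulation. Performance status of 50 is eligible, and Appendix III describes Lansky 50 as a child who lies around much of the day.
- After surgery: the rehabilitation protocol in section 5.2 allows casting to be extended in steps until healing is satisfactory, and ties full weight-bearing to a RUST score of 9 or more.
- On the other side: section 5.2 foresees braced partial weight-bearing from 3 months, and section 5.5 allows the test in a brace or with an adaptive device.

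So some children may have no time, but a RUST score below 9 does not in itself prevent the test.

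**2. What do the planned analyses do with such a child?**
- Paired t-test: it needs both values, so the child is lost. This follows directly.
- Mixed models: any other visits are kept, on the assumption that the missing value is predictable from what was observed. That is doubtful when the value is missing because the child cannot walk.
- Sensitivity analysis for inevaluable patients (section 6.2): it assigns RUST category 4-7 and gives no walk score. The section 10.5 to which it refers for the definition of evaluable is not in the document.

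**3. Size, under assumed rates.** Let qC and qB be the proportions unable to walk in the control and BMP-2 groups, with walkers identical in both. Walkers only: P(BMP-2 better) = 0.50. With non-walkers ranked worst and ties counted as half:

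P = (1 − qB)·qC + 0.5·[(1 − qB)(1 − qC) + qB·qC] = 0.5 + (qC − qB)/2

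| qC | qB | Walkers only | Worst rank |
|---|---|---|---|
| 10% | 5% | 0.50 | 0.525 |
| 20% | 10% | 0.50 | 0.55 |
| 30% | 15% | 0.50 | 0.575 |

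These rates are not in the documents. As a deliberately pessimistic proxy, the design figures in section 6.2 put 33% of controls and 15% of BMP-2 children at RUST 4-7 at 12 months.
- All of them unable: P = 0.5 + 0.18/2 = 0.59. Mean speed with zeros is 0.67 v 0.85 of the walkers' speed, and 0.85/0.67 = 1.27.
- Half of them unable: P = 0.5 + (0.165 − 0.075)/2 = 0.545. Mean speed is 0.835 v 0.925, and 0.925/0.835 = 1.11.

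**4. The 20% benchmark.** Speed = 10 m / time.
- 20% faster: time × 1/1.2 = 0.833, or 16.7% fewer seconds.
- 20% slower: time × 1/0.8 = 1.25, or 25% more seconds.

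The order of averaging also matters. Trials of 8, 10 and 15 s have mean 11 s, and 10/11 = 0.909 m/s; the mean of the three speeds is 0.972 m/s.

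**5. Age.** Validation is cited from 4 and entry is from 2, so ages 2-3 fall outside the cited range. Their number is not given.

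**The case against.** The strongest objection is that few children may be affected. Partial weight-bearing in a brace from 3 months, assistive devices and the discretionary nature of longer casting mean that many poorly healed children can be tested at 6 and 12 months. This stands. A reader might infer that the worst-healing children as a group have no value; the documents do not support that.

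A reader might also infer that function in non-walkers goes unmeasured. It does not. The PODCI has mobility and physical-function domains and is completed by the parent for ages 2-10, and sections 5.3 and 5.8 record weight-bearing ability. The walk is the only timed performance test, not the only functional measure. But neither source supplies a walk score.

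It is tempting to say that the mismatch between seconds and speed misclassifies responders. No analysis in section 6 uses the 20% benchmark, the text states it in speed, and over a fixed distance the conversion is exact. What remains is a need to name one scale.

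On age, the floor of 4 years for the Faces Pain Scale in section 5.4 is not a close parallel: the reason given there is the lack of a validated self-report scale for younger children. A stopwatch test is different, and dropping ages 2-3 from the main analysis would cost patients in a trial of 36-52.

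Finally, loss of non-walkers is inferred from silence, and section 6.2 does not spell out a between-group test of the walk. The inference is nevertheless direct for the paired t-test, and the illustration applies to any comparison of times between groups.

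**Conclusion.** The point holds in a limited form. The walk score is undefined for a child who cannot complete 10 m because of the leg, no rule fills the gap, and the reason for the gap is related to healing. The paired t-test loses such children; the mixed models keep their other visits only under a doubtful assumption. Both failure to recover and recovery from not walking can be hidden.

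The size is unknown. With inability of 10-30% in controls and half that with BMP-2, the hidden difference in P(BMP-2 better) is 0.025 to 0.075. This assumes identical walkers in both groups. The pessimistic proxy gives 0.09.

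This concerns a secondary outcome. The primary RUST comparison is touched only through the imputation model, and only if that model is used. The scale of the 20% benchmark and the under-4 age range are smaller matters of specification. The change is worth making because it is cheap and gives a value to children whom the plan now leaves without one.

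**What to change.** In sections 5.5, 5.8 and 6.2:
- Derive walking speed as 10 m divided by the mean time in seconds, and make it the analysed score.
- Score 0 m/s, as worst rank, for a child unable to walk 10 m because of the leg.
- Record a reason code for every missing walk.
- Analyse the walk and its change by rank methods.
- Report a sensitivity analysis that treats a child not permitted to walk first as 0 and then as missing. Permission may rest with the surgeon, who knows the treatment (section 4.2.3), so this state should not be fixed as 0 in a single analysis.
- If the 20% benchmark is used, apply it to speed and only in children with a non-zero baseline, since percentage change from 0 is undefined. Report moves between unable and able separately.
- Keep all ages in the main analysis, and show children under 4 separately as a sensitivity analysis.

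The cost is one form field and a derived variable. Speed with zeros is skewed, so means are harder to interpret.
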